## Adverse Event Severity and Relationship to Study Drug

The investigator will classify AEs according to the Rheumatology Common Toxicity Criteria v.2.0 ([Appendix I](#)).

The investigator will use the following definitions to assess the relationship of the AE to the use of study drug:

|                                  |  |
|----------------------------------|--|
| Reasonable Possibility    | After consideration of factors including timing of the event, biologic plausibility, clinical judgment, and potential alternative causes, there is sufficient evidence (information) to suggest a causal relationship.   |
| No Reasonable Possibility | After consideration of factors including timing of the event, biologic plausibility, clinical judgment, and potential alternative causes, there is insufficient evidence (information) to suggest a causal relationship. |

## Pregnancy

While not an AE, pregnancy in a study subject must be reported to AbbVie within 1 working day after the site becomes aware of the pregnancy. Subjects who become pregnant during the study must be discontinued (Section 5.5). If a pregnancy occurs in a study subject or in the partner of a study subject, information regarding the pregnancy and the outcome will be collected.

In the event of pregnancy occurring in a subject's partner during the study, written informed consent from the partner must be obtained prior to collection of any such information. AbbVie will provide a separate consent form for this purpose. Pregnancy in a subject's partners will be collected from the date of the first dose through 70 days following the last dose of study drug.

The pregnancy outcome of an elective or spontaneous abortion, stillbirth or congenital anomaly is considered a SAE and must be reported to AbbVie within 24 hours after the site becomes aware of the event.

## 6.2 Toxicity Management

---

The management of specific AEs and laboratory parameters is described in [Table 2](#) and in the Operations Manual ([Appendix K](#)).

The toxicity management of the AEs including AEs of special interest consists of safety monitoring (review of AEs on an ongoing basis, and periodical/ad hoc review of safety issues by a safety data monitoring committee), interruption of study drug dosing with appropriate clinical management if applicable, and discontinuation of the subjects from the study drug. The management of specific AEs and laboratory parameters is described below.

For subjects who discontinued study drug but continued study participation and are on standard of care therapies, these toxicity management requirements do not apply (including alerts from the central lab) and any intolerability to standard of care therapies should be managed by the prescribing physician.

### Management of Hypersensitivity and Serious Allergic Reactions

Subjects should be closely monitored and assessed for the development of signs and symptoms of hypersensitivity reactions, including anaphylaxis. Drug administration (ABBV-3373) should be done slowly over 15 – 30 minutes (via infusion line or infusion pump; the study drug can be diluted in 50 – 100 mL isotonic saline solution for this administration), and subjects should be observed for at least 30 minutes thereafter. Study drug should be discontinued and appropriate therapy be instituted if a subject develops clinically significant hypersensitivity reactions.

#### *Hypersensitivity Testing*

In the event of a suspected systemic post-dose hypersensitivity reaction, if the clinical situation allows, every effort should be made to obtain a serum sample within 2 hours but no later than 6 hours from symptom onset for additional blood tests (e.g, tryptase, ADA, nAb, total IgE, total hemolytic complement, etc.). Additional details regarding hypersensitivity testing can be found in the Operations Manual, Section 3.12 ([Appendix K](#)).

### Management of Serious Infections

Subjects should be closely monitored for the development of signs and symptoms of infection during and after treatment with study drug. Study drug should be interrupted if a subject develops a serious infection or a serious opportunistic infection. A subject who develops a new infection during treatment with study drug should undergo prompt diagnostic testing appropriate for an immunocompromised subject. As appropriate, antimicrobial therapy should be initiated, and the subject should be closely monitored. Study drug may be restarted once the infection has been successfully treated. Subjects who develop active TB must be permanently discontinued from study drug.

### Management of Malignancy

Subjects who develop malignancy other than NMSC or carcinoma in-situ of the cervix must be discontinued from the study drug. Information including histopathological results should be queried for the confirmation of the diagnosis.

### Management of Demyelinating Disease

Subjects must be discontinued from study drug with new onset or exacerbation of clinical symptoms and/or radiographic evidence of central nervous system demyelinating disease (including multiple sclerosis), optic neuritis, and peripheral demyelinating disease (including Guillain Barré syndrome).

### Management of Hypertension

Subjects should be closely monitored for the development of hypertension before and 30 minutes after treatment with study drug. Study drug should be interrupted if a subject develops serious hypertension in which case they should be monitored under standard of care.

### Management of Hyperglycemia

Subjects should be closely monitored for the development of hyperglycemia during and after treatment with study drug. Study drug should be interrupted if a subject develops a serious hyperglycemia in which case they should be monitored under standard of care.

### Management of GC-Induced Adrenal Insufficiency

High dose or long term use of corticosteroids can produce reversible HPA axis suppression with the potential for GC insufficiency after withdrawal of treatment. Drug-induced secondary adrenocortical insufficiency may be minimized by gradual reduction of dosage. This type of relative insufficiency may persist for months after discontinuation of therapy; therefore, hormone therapy should be reinstated in any situation of stress occurring during that period.

### Management of Select Laboratory Abnormalities

For any given laboratory abnormality, the investigator should assess the subject, apply the standard of care for medical evaluation and treatment following any local guidelines. Specific toxicity management guidelines for selected abnormal laboratory values are described in [Table 2](#), and may require a supplemental eCRF to be completed (Section 6.1 [Complaints and AEs]). All abnormal laboratory tests that are considered clinically significant by the investigator will be followed to a satisfactory resolution. If a repeat test is required per [Table 2](#), the repeat testing must occur as soon as possible.

**Table 2. Specific Toxicity Management Guidelines for Abnormal Laboratory Values**

| Laboratory Parameter | Toxicity Management Guideline  |
|----------------------|--|
| Hemoglobin           | 
 
• If hemoglobin < 8 g/dL interrupt study drug dosing and confirm by repeat testing with new sample
 
• If hemoglobin decreases <math>\geq 3.0</math> g/dL from BL, without an alternative etiology, interrupt study drug dosing and confirm by repeat testing with new sample.
 
• If hemoglobin decreases <math>\geq 3.0</math> g/dL from BL and an alternative etiology is known, the subject may remain on study drug at the investigator's discretion.
 
• If confirmed, continue to withhold study drug until hemoglobin value returns to normal reference range or its BL value.
 
 |

| Laboratory Parameter             | Toxicity Management Guideline  |
|----------------------------------|--|
| Absolute neutrophil count (ANC)  | 
 
• If confirmed < 1000/<math>\mu</math>L by repeat testing with new sample, interrupt study drug dosing until ANC value returns to normal reference range or its BL value.
 
• Discontinue study drug if confirmed < 500/<math>\mu</math>L by repeat testing with new sample.
 
  |
| Absolute lymphocyte counts (ALC) | 
 
• If confirmed < 500/<math>\mu</math>L by repeat testing with new sample, interrupt study drug dosing until ALC returns to normal reference range or its BL value.
 
  |
| Total white blood cell count     | 
 
• If confirmed < 2000/<math>\mu</math>L by repeat testing with new sample, interrupt study drug dosing until white blood cell count returns to normal reference range or its BL value.
 
  |
| Platelet count                   | 
 
• If confirmed < 50,000/<math>\mu</math>L by repeat testing with new sample, interrupt study drug dosing until platelet count returns to normal reference range or its BL value.
 
  |
| AST or ALT                       | 
 
• Interrupt study drug if confirmed ALT or AST > 3 <math>\times</math> ULN by repeat testing with new sample and either a total bilirubin > 2 <math>\times</math> ULN or an international normalized ratio (INR) > 1.5.               
 
• A separate blood sample for INR testing will be needed to measure INR at the time of repeat testing for ALT or AST. A repeat test of INR is not needed for determination if above toxicity management criteria are met.
 
 
 
• Interrupt study drug if confirmed ALT or AST > 3 <math>\times</math> ULN by repeat testing with new sample along with appearance of fatigue, nausea, vomiting, right upper quadrant pain or tenderness, fever, rash, and/or eosinophilia (> 5%).
 
• Interrupt study drug if confirmed ALT or AST > 5 <math>\times</math> ULN by repeat testing with new sample for more than 2 weeks.
 
• Interrupt study drug if confirmed ALT or AST > 8 <math>\times</math> ULN by repeat testing with new sample.
 
 
Subjects who meet any of the above criteria should be evaluated for an alternative etiology of the ALT or AST elevation and managed as medically appropriate. The investigator should contact the AbbVie TA MD to discuss the management of a subject when an alternative etiology has been determined. The alternative etiology should be documented appropriately in the eCRF; study drug should be discontinued if no alternative etiology can be found and ALT or AST elevations persist.
 
For any confirmed ALT or AST elevations > 3 ULN, complete the appropriate supplemental hepatic eCRF(s).
 
 
• Subjects with HBc Ab+ (irrespective of HBs Ab status) and negative HBV DNA PCR testing at Screening who develop the following should have HBV DNA PCR testing performed within one week:               
 
• ALT > 5 <math>\times</math> ULN OR
 
• ALT or AST > 3 <math>\times</math> ULN and either a total bilirubin > 2 <math>\times</math> ULN or INR > 1.5 OR
 
• ALT or AST > 3 <math>\times</math> ULN along with clinical signs of possible hepatitis.
 
 
 
 
A positive result for HBV DNA PCR testing will require immediate interruption of study drug (unless not acceptable by local practices) and a hepatologist consultation should occur within 1 week for recommendation regarding subsequent treatment.
 |

| Laboratory Parameter         | Toxicity Management Guideline   |
|------------------------------|---|
| Serum Creatinine             | 
 
If serum creatinine is <math>> 1.5 \times</math> the BL value and <math>> \text{ULN}</math>, repeat the test for serum creatinine (with subject in an euvoletic state) to confirm the results. If the results of the repeat testing still meet this criterion, then interrupt study drug and re-start study drug once serum creatinine returns to <math>\leq 1.5 \times \text{BL}</math> value and <math>\leq \text{ULN}</math>.
 
 
For the above serum creatinine elevation scenario, complete the appropriate supplemental renal eCRF(s).
 |
| Creatine Phosphokinase (CPK) | 
 
If confirmed CPK value <math>\geq 4 \times \text{ULN}</math> and there are no symptoms suggestive of myositis or rhabdomyolysis, the subjects may continue study drug at the investigator's discretion.
 
If CPK <math>\geq 4 \times \text{ULN}</math> accompanied by symptoms suggestive of myositis or rhabdomyolysis, interrupt study drug and contact AbbVie TA MD.
 
 
For the above CPK elevation scenarios, complete supplemental increased CPK eCRF.
  |

Ab = antibody; ALC = Absolute lymphocyte counts; ALT = alanine aminotransferase; ANC = absolute neutrophil count; AST = aspartate aminotransferase; BL = baseline; CPK = creatine phosphokinase; DNA = deoxyribonucleic acid; eCRF = electronic case report form; HB = hepatitis B; HBV = hepatitis B virus; INR = international normalized ratio; PCR = polymerase chain reaction; TA MD = Therapeutic Area Medical Director; ULN = upper limit of normal

### Management of ECG Abnormality

Subjects should be discontinued for an ECG change considered clinically significant OR a confirmed absolute QT interval corrected for heart rate using Fridericia's correction formula (QTcF) value  $> 500$  msec.

## 7 STATISTICAL METHODS & DETERMINATION OF SAMPLE SIZE

### 7.1 Statistical and Analytical Plans

The statistical methods provided in this protocol will be focused on primary and secondary analyses. Complete and specific details of the statistical analysis will be described in the Statistical Analysis Plan (SAP). All statistical analyses will be performed using SAS (SAS Institute Inc., Cary, North Carolina, USA).

### 7.2 Definition for Analysis Populations

The Full Analysis Set (FAS) includes all randomized subjects who received at least 1 dose of the study drugs. The FAS will be used for all efficacy analyses. Subjects will be grouped according to treatment as randomized. The Per-Protocol Analysis Set represents a subset of the FAS and consists of all FAS subjects without any major violations. Additional analysis may be conducted on the Per-Protocol Analysis Set as deemed appropriate, in order to evaluate the impact of major protocol violations on the primary endpoint.

The Safety Analysis Set consists of all subjects who received at least 1 dose of the study drugs. For the Safety Analysis Set, subjects are grouped based on the treatment actually received, regardless of the treatment randomized.

## 7.3 Statistical Analyses for Efficacy

---

### Primary Endpoint Analysis

Analysis of the primary endpoint will be conducted on the FAS based on treatment as randomized.

The primary endpoint is the change from BL in DAS28(CRP) at Week 12. The historical mean and standard deviation of the change from BL in DAS28(CRP) at Week 12 in adalimumab 80 mg eow are estimated to be  $-2.13$  and  $1.35$  respectively based on a meta-analysis of 3 historical adalimumab studies (Studies DE007, DE009, and DE011).

The first comparison in order to achieve the first primary objective of assessing the efficacy of ABBV-3373 is to compare change from BL in DAS28(CRP) at Week 12 in the ABBV-3373 group with  $-2.13$ , the adalimumab 80 mg eow historical mean change from BL at Week 12 based on the meta-analysis. The treatment mean change from BL and 90% confidence interval of ABBV-3373 will be estimated from Mixed Effect Model Repeated Measurements (MMRM) method including up to Week 12 data with treatment group, visits, treatment-by-visit interaction, BL values of the primary endpoint, and stratification factors with observed case (OC) data. The study will be declared positive if the comparison is significant and favoring ABBV-3373.

In order to achieve the second primary objective of comparing clinical efficacy of ABBV-3373 with adalimumab and to test the concept that an anti-TNF ADC has the potential to provide superior efficacy than the traditional anti-TNF antibody in RA, the second comparison is to compare ABBV-3373 with adalimumab for the primary efficacy endpoint with a Bayesian historical data borrowing approach. The same MMRM model as described in the first comparison will be used to estimate in-study mean and standard deviation. Informative normal prior for adalimumab will be determined based on historical adalimumab data and a non-informative prior will be used for ABBV-3373. The prior distributions and estimates from MMRM model will be combined to construct the posterior distributions which will be used for comparison between ABBV-3373 and adalimumab.

If the adalimumab group mean is not comparable with historical adalimumab data, for example, the confidence intervals of the mean based on historical and in-trial data don't overlap, the Bayesian approach based on historical data will not be performed, and the mean difference in change from BL in DAS28(CRP) at Week 12 between the ABBV-3373 group and adalimumab will be estimated only based on in-study data with the MMRM model described above.

Historical data borrowing will only apply to the primary endpoint.

To address the secondary objectives of assay sensitivity, a synthetic placebo arm will be created with the propensity score matching approach using historical placebo subjects from similar trials with subject-level data. Details will be provided in the SAP.

## Secondary Endpoints and Additional Endpoints Analyses for BL to Week 12

For the first 12 weeks of treatment period, continuous efficacy variables will be analyzed using an MMRM method. Categorical efficacy variables will be analyzed using the Cochran-Mantel-Haenszel (CMH) test controlling for stratification variables. Non-responder imputation (NRI) will be used for primary inference purpose. Observed Case data will be summarized descriptively as a sensitivity analysis.

## Additional Endpoints Analyses up to Week 24

Statistical inference of additional continuous endpoints at each visit up to Week 24 will be conducted using analysis of covariance (ANCOVA) with treatment and stratification factors as the fixed factors and the corresponding BL value as the covariate. Additional categorical efficacy variables up to Week 24 will be analyzed using the same CMH test as for the binary secondary endpoint analysis.

Details on the analyses of the primary and other efficacy endpoints will be provided in the SAP.

## Sample Size Estimation

The primary endpoint is the mean change of DAS28(CRP) from BL at Week 12. Two comparisons are considered. The first one is to compare mean change in DAS28(CRP) of the ABBV-3373 group to that of historical adalimumab 80 mg eow, which is  $-2.13$ . Assuming a mean DAS28(CRP) change from BL of  $-2.769$  to  $-2.982$  for ABBV-3373 (corresponding to 30% to 40% more reduction than historical adalimumab) and a standard deviation of 1.35, 30 subjects on ABBV-3373 will provide an approximate 81% to 96% power with a one-sample t-test and one-sided  $\alpha = 0.05$  significance level.

The second comparison is between ABBV-3373 arm and adalimumab arm with borrowed historical adalimumab data using a Bayesian approach. When considering borrowing historical data, the planned sample size is 45 subjects (30 in ABBV-3373 and 15 in adalimumab). The study will be considered successful if the posterior probability of mean difference  $< 0$  is larger than 95%, i.e.,:

$$P(\mu_{ABBV-3373} - \mu_{Adalimumab} < 0 | data) > 0.95.$$

Based on the historical mean and standard deviation from adalimumab meta-analysis, a prior distribution for adalimumab is  $N(-2.13, 0.246^2)$  corresponding to the 30 historical subjects borrowed. A noninformative prior for ABBV-3373 treatment group will be set. Given the mean change from BL in DAS28 (CRP) is  $-2.13$  for adalimumab, the probability to claim the study success is approximately 66% to 88% if the mean change from BL in DAS28 (CRP) is  $-2.769$  to  $-2.982$  for ABBV-3373 (i.e., 30% to 40% more reduction than historical adalimumab), with at least 45 subjects for adalimumab (15 in-trial and at least 30 borrowed) and 30 subjects for ABBV-3373. If both ABBV-3373 and adalimumab groups have the same mean change from BL of  $-2.13$ , the probability to claim study success (equivalent to type I error rate) is approximately 0.03 with the same sample sizes. In the event that adalimumab variability precludes historic data borrowing, using only the in-study 15 adalimumab subjects and 30 ABBV-3373 subjects will provide 43% to 63% power when ABBV-3373 in 30% to 40% more reduction than adalimumab respectively.

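### The 0.03 called the type I error rate of the Bayesian comparison holds only if both true means equal the prior mean of −2.13; if both arms do one prior SD better, the error is about 10%

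*Protocol*

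**What the plan says.** The second primary comparison sets ABBV-3373 against adalimumab with borrowed historical data. Protocol section 7.3, Sample Size Estimation, fixes its design:

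- **Adalimumab prior.** "Based on the historical mean and standard deviation from adalimumab meta-analysis, a prior distribution for adalimumab is" normal with mean −2.13 and SD 0.246, "corresponding to the 30 historical subjects borrowed".
- **ABBV-3373 prior.** "A noninformative prior for ABBV-3373 treatment group will be set".
- **Success rule.** "The study will be considered successful if the posterior probability of mean difference" below zero exceeds 95%.
- **Null scenario.** A single one is given, in which the true means of both arms coincide with the prior mean. For it the protocol writes: "the probability to claim study success (equivalent to type I error rate) is approximately 0.03 with the same sample sizes". No other common mean is considered.

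Section 7.3, Primary Endpoint Analysis, adds a comparability rule. Borrowing is dropped if in-trial adalimumab does not match history; the example given is that "the confidence intervals of the mean based on historical and in-trial data" fail to overlap. The difference between arms then "will be estimated only based on in-study data with the MMRM model described above". The protocol gives neither the confidence level nor the width of the historical interval.

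**The concern.** A type I error rate describes the whole null hypothesis, which here is equal true means at any value. Without borrowing, the common value would cancel out of the comparison. With a fixed informative prior on one arm only, it does not: the adalimumab estimate is pulled towards −2.13 while the ABBV-3373 estimate is not. If both arms respond better than −2.13 for reasons unrelated to the drug (different patients, sites, era or background care), that improvement is credited in full to ABBV-3373 but only in part to adalimumab.

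This comparison carries the claim of superiority over adalimumab. A reader told that the false-positive risk is 3% will give a positive result more credit than the design earns if both arms outperform history.

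**Working it through.** **Inputs** (protocol section 7.3): SD 1.35; 30 subjects on ABBV-3373 and 15 on adalimumab; adalimumab prior mean −2.13, SD 0.246; flat prior for ABBV-3373; posterior threshold 0.95.

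**Model** (conjugate normal, SD known)

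- Prior variance: 0.246² = 0.0605. In-trial adalimumab variance: 1.35²/15 = 0.1215.
- Weight on the prior: (1/0.0605)/(1/0.0605 + 1/0.1215) = 0.668. Weight on the 15 concurrent subjects: 0.332.
- Posterior variance of the adalimumab mean: 0.0404. Variance of the ABBV-3373 mean: 1.35²/30 = 0.0608.
- Posterior SD of the difference: √(0.0404 + 0.0608) = 0.318. Success requires a posterior mean difference below −1.645 × 0.318 = −0.523.
- Sampling SD of the posterior mean difference: √(0.0608 + 0.332² × 0.1215) = 0.272.

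**The protocol's own figures are reproduced**

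- Both means −2.13: Φ(−0.523/0.272) = 0.027 (0.031 by simulation with estimated SD), against about 0.03 stated.
- ABBV-3373 at −2.769: Φ((−0.523 + 0.639)/0.272) = 66.5%. At −2.982: Φ((−0.523 + 0.852)/0.272) = 88.6%. The protocol states 66% to 88%.

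**Equal true means away from −2.13.** If both arms are better by d, the expected posterior difference is −0.668d, so P(success) = Φ((−0.523 + 0.668d)/0.272).

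| Common shift from −2.13 | P(success), arms equal |
|---|---|
| 0.5 worse | 0.001 |
| 0.25 worse | 0.006 |
| none | 0.027 |
| 0.113 better | 0.050 |
| 0.246 better (one prior SD) | 0.094 |
| 0.5 better (2.0 prior SDs) | 0.243 |

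Under the protocol's own prior, the probability of an adalimumab mean more than 0.1125 better is 1 − Φ(0.1125/0.246) = 0.32. Averaged over that prior, the error is 5.0%.

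**With the comparability rule.** The missing details were filled by assumption: 90% or 95% intervals, a historical standard error of 0, 0.10 or 0.246, SD estimated on 43 degrees of freedom, and a one-sided 0.05 in-trial t-test as fallback. At least 1,000,000 simulated trials were run per scenario. A standard error of 0 is a limiting case, with no historical interval at all.

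| Type I error | 90%, SE 0 | 90%, SE 0.10 | 90%, SE 0.246 | 95%, SE 0 | 95%, SE 0.10 | 95%, SE 0.246 |
|---|---|---|---|---|---|---|
| 0.5 worse | 0.050 | 0.047 | 0.035 | 0.048 | 0.042 | 0.019 |
| 0.25 worse | 0.047 | 0.038 | 0.019 | 0.041 | 0.026 | 0.011 |
| No shift | 0.049 | 0.040 | 0.033 | 0.042 | 0.034 | 0.031 |
| 0.246 better | 0.097 | 0.097 | 0.097 | 0.097 | 0.097 | 0.097 |
| 0.5 better | 0.195 | 0.221 | 0.240 | 0.215 | 0.235 | 0.243 |
| Averaged over the prior | 0.069 | 0.064 | 0.058 | 0.066 | 0.060 | 0.055 |
| Shift where 5% is passed | 0.015 | 0.076 | 0.095 | 0.064 | 0.091 | 0.097 |

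The rule does little because it rarely acts: at a shift of 0.5 it still borrows in 59% to 97% of trials.

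**Power if both arms do worse.** With adalimumab 0.5 worse than −2.13 and the differences between arms held at −0.639 and −0.852, power with the rule is 23% to 40% and 50% to 61%. At −2.13 the same differences give the stated 66% and 88%.

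**The case against.** The strongest reply is that the sentence states its condition. It opens with both means at −2.13, and 0.03 is correct there; no formula, test or decision rule is wrong. That stands, and the figure is not disputed. The parenthesis, however, turns a conditional figure into a general error rate, and a reader will carry 3% away as the property of the rule.

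Second, the error is not inflated everywhere. One prior SD worse gives 0.6% without the comparability rule, and the average over the protocol's prior is 5.0%, which matches the 95% threshold. This also stands. But an average of 5.0% (5.5% to 6.9% with the rule) is not 3% either, and a frequentist type I error rate is not a prior average.

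Third, the larger figures need assumed drift, and a historical standard error of 0 is not a natural reading of an interval-overlap rule. Leaving that case out, the no-shift error is 3.1% to 4.0% and 5% is passed at 0.076 to 0.097 better. The result at one prior SD is unchanged. The overlap criterion is itself only an example, so other comparability rules might behave differently.

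Fourth, a table of operating characteristics may belong in the SAP, which was not available here. Its absence from the protocol is therefore not counted as a fault; the wording is wrong whatever the SAP contains.

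**Conclusion.** The concern holds. The stated 0.03 is the success probability at a single point of the null hypothesis and not the type I error rate of the second comparison. In the model that reproduces the protocol's null and power figures, the error is 9.4% (9.7% with estimated SD) when both arms do 0.246 better than −2.13. The overlap rule leaves it at about 9.7% under all six readings tried. At 0.5 better it is 19% to 24% with the rule. In the other direction it stays at or below about 5%, at a cost in power.

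These sizes rest on SD 1.35, the planned 30 and 15 subjects, and assumed shifts, since the protocol quantifies no drift. The one-SD shift is on the scale of uncertainty that the protocol's own prior expresses.

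The consequence is limited to how the second comparison is read. This is a 45-subject Phase 2a concept test, and Primary Endpoint Analysis declares the study positive on the first comparison. It should be fixed, but it does not undermine the design.

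**What to change.** In section 7.3, Sample Size Estimation, replace the parenthetical label with wording such as: *This applies when the true in-trial adalimumab mean is −2.13. It is not a bound on the type I error rate, which is higher if both groups do better than −2.13.*

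Report type I error and power of the full procedure, including the comparability rule, for common shifts such as ±0.25, ±0.5 and ±0.75, either there or by reference to the SAP. State the confidence level and historical standard error used in those simulations.

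The cost is one reworded sentence and a short simulation. The prior, success threshold, sample size and borrowing rule need not change. The only downside is a less favourable stated error figure.
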